1. PROTOCOL SUMMARY

1.1 Table 1: Schedule of Activities (SoA)

Dose		1	2	3	4	5	6	7	8	9	10		
Days (± 3 days of windows period)	-7 to 0	1	15	29	43	57	71	85	99	113	127	141	230
Week (1st day of week)		0	2	4	6	8	10	12	14	16	18	Last day of week 20	
Visit	1	2	3	4	5	6	7	8	9	10	11	12	13
	Screening Period						Evalua	ation P	hase				Follow-up period
	Screening Visit				Eva	luatio	n Visit	(2-11))			End of Evaluation Visit	End of Study Visit
Informed Consent Form	X												
Eligibility Criteria	X	X											
Demography and history of tobacco and alcohol use	X												
Medical and surgical history (including all treatments for NSCLC/mUC)	X												
Physical examination	X	X		Targ	eted pl	ysical	exam (based	on sym	ptoms)		X	
Vital signs (pre and post-infusion vital signs assessments; see Section 6.4.8)		X	X	X	X	X	X	X	X	X	X	X	
Urine Pregnancy Test	X												
Weight		X		X		X		X		X			
World Health Organization performance status	X	X	X	X	X	X	X	X	X	X	X	X	
Concomitant medications	X	X	X	X	X	X	X	X	X	X	X	X	
Disease Characteristics Assessment		X			X			X			X	X	
Adverse event/serious adverse event assessment		X	X	X	X	X	X	X	X	X	X	X	X
Electrocardiogram (before dosing of IP)		X				X				X			
Haematology		X	X	X	X	X	X	X	X	X	X	X	
Serum chemistry (LFT, RFT, Electrolytes)		X	X	X	X	X	X	X	X	X	X	X	
Urine Routine and microscopy		X	X	X	X	X	X	X	X	X	X	X	
Thyroid function tests (TSH, T3 and T4) ^a		X				X				X		X	
IP Administration		X	X	X	X	X	X	X	X	X	X		

a. Except screening visit, free T3 and free T4 will only be measured if TSH is abnormal or if there is clinical suspicion of an AE related to the endocrine system.

1.2 Synopsis

Protocol Title: A prospective, multicenter, Phase-IV clinical trial to assess safety of Durvalumab in Indian adult patients with locally advanced, unresectable non-small cell lung cancer (NSCLC).

Version: 4.1 Date: 12 October 2022

Study site(s) and number of patients planned

No. of total screened patients: Approximately 120 No. of total enrolled patients: Approximately 100

No. of study sites ~ 10

Total planned Study period	
Estimated date of first patient in	Q4 – 2021
Estimated date of last patient in	Q4 – 2022
Estimated date of last patient last visit	Q3 – 2023
Estimated date of data base lock	Q3 – 2023
Clinical study report	Q4 – 2023

Rationale

The present study is a Phase IV safety study of durvalumab to be conducted in compliance with a condition of approval specified by the Health Authorities of India. Approval in India has been granted for the use of durvalumab for the treatment of patients with locally advanced, unresectable non-small cell lung carcinoma (NSCLC) whose disease has not progressed following platinum-based chemoradiation therapy. As a condition of approval, AstraZeneca is required to conduct a Phase IV clinical trial so that adverse reactions related to treatment with durvalumab are reported to the Health Authorities in India and subsequently, any regulatory action resulting from the review of reported adverse reactions should be complied with by the Sponsor.

The present study will provide information on the safety profile of durvalumab for the treatment of locally advanced NSCLC in Indian patients in accordance with the requirements of the Health Authorities of India.

Objectives and Endpoints

Primary objective:	Primary Outcome Measure:
To assess the safety of durvalumab among locally advanced unresectable non-small cell lung carcinoma in Indian patients	Number, frequency and proportion of patients with adverse events (AEs), serious adverse events (SAEs) and AEs of special interest (AESI) including interstitial lung disease/pneumonitis-like events, and onstudy deaths.

AstraZeneca

Overall design:

This is a Phase IV, open-label, single arm, multi-center, prospective study to be conducted in India. Two cohorts of patients will be included in the current study patients with locally advanced, unresectable NSCLC whose disease has not progressed following platinum-based chemoradiation therapy (N= 100). Potential patients will undergo eligibility determination within 7 days prior to first dose. Patients who meet the protocol-defined inclusion/exclusion criteria will be prospectively enrolled in a sequential manner at 10 centres in India. All enrolled patients will be treated with durvalumab administered intravenously over 60 minutes at 10 mg/kg every 2 weeks. The treatment period for this study is 20 weeks, which corresponds to 10 doses of study drug administration. Treatment will continue as long as clinical benefit is observed for a maximum of 20 weeks or either of the criteria defined in section 7 are met, whichever is earlier. Patients who are observed to continue to receive clinical benefit from durvalumab at end of Week 20 (as defined in SoA) will continue treatment in post-trial phase (defined in section 6.7). Any patient who discontinues treatment with durvalumab before end of Week 20 on study will be followed for 90 days after discontinuation of study drug or until the start of alternate treatment intervention, whichever is earlier.

Safety will be evaluated throughout the evaluation phase and during the follow up of patients who discontinue treatment before end of Week 20 by physical exams including vital signs, AE/SAE monitoring, laboratory evaluations and recording of concomitant medications.

Screening Phase (Visit 1)

Patients, or their legally acceptable representative, will provide written informed consent before any trial-specific procedures are performed. During the Screening Phase, eligibility criteria will be reviewed and a complete clinical evaluation will be performed as specified in the Time and Event Schedule. Screening procedures will be performed 7 days before first dose (week 0, day 1). All baseline disease characteristics will be captured based evaluation performed as a part of routine clinical practice. The documented tests that are required before consideration of patient for durvalumab treatment based on the local prescribing information by investigator must have been performed 28 days before first dose (week 0, Day 1).

Evaluation Phase (Visit 2 To 11)

The Evaluation Phase will extend from first dose (Week 0, Day 1) to end of Week 20; or until study drug discontinuation due to either disease progression or unacceptable toxicity; or other reasons whichever occurs first, as listed in Section 7. Details of the procedures performed during the Evaluation Phase are outlined in the Time and Events Schedules. Patients will be closely monitored for adverse events and other safety evaluations including laboratory investigations, concomitant medications. If disease progression is diagnosed before end of week 20 then the patient will discontinue study drug with completion of the End-of-Evaluation Visits on the day of progression, and will enter the safety Follow-up Phase.

End-Of- Evaluation Visit (EoE)

An End-of- Evaluation Visit is to be scheduled on end of week 20 (Day 141) of the study. In a case where patient discontinues the study treatment for any reason listed in Section 7.1 before 20

Drug Substance - DURVALUMAB Study Code - D133HC00003 Version 4.1, Date: 12 October 2022

weeks, last visit of the patient will be considered as End-of- Evaluation visit. Every effort should be made to conduct the telephonic End-of-Study Visit before the patient starts subsequent treatment.

Follow Up Phase (End-Of-Study)

A telephonic follow-up will be conducted 90 days after the EOE Visit. This will be considered as End-of-Study visit.

The observation period including the Evaluation Phase and safety Follow-up phase will be up to a maximum duration of approximately 230days for each patient.

PATIENT POPULATION

Inclusion criteria

Patients are eligible to be included in the study only if all of the following inclusion criteria and none of the exclusion criteria apply:

- 1. Provision of signed, written and dated informed consent prior to any study specific Procedures
- 2. Male or female aged 18 years or older
- 3. As per local prescribing information and in view of positive benefit-risk assessment, patient prescribed Durvalumab treatment as per independent clinical judgment of treating physician for either treatment for locally advanced, unresectable non-small cell lung carcinoma whose disease has not progressed following platinum-based chemoradiation therapy (N= 100)

The ICF process is described in Appendix A 3.

Exclusion criteria

- 1. Concurrent enrolment in another clinical study, unless it is an observational (non-interventional) clinical study or the follow-up period of an interventional study
- 2. Current or prior use of immunosuppressive medication within 14 days before the first dose of study drug, with the exceptions of intranasal and inhaled corticosteroids or systemic corticosteroids at physiological doses, which are not to exceed 10 mg/day of prednisone, or an equivalent corticosteroid. Systemic steroid administration required to manage toxicities arising from radiation therapy delivered as part of the chemoradiation therapy for locally advanced NSCLC is allowed.
- 3. Prior exposure to any anti-PD-1 or anti-PD-L1 antibody including durvalumab.
- 4. For NSCLC cohort only:
 - a. Mixed small cell and non-small cell lung cancer histology
 - b. Any unresolved toxicity CTCAE > Grade 2 from the prior chemoradiation therapy.
 - c. Patients with ≥Grade 2 pneumonitis from prior chemoradiation therapy

5. Active or prior documented autoimmune disease within the past 2 years, inflammatory bowel disease (eg, Crohn's disease, ulcerative colitis), primary immunodeficiency, organ transplant that requires therapeutic immunosuppression, hypersensitivity to study drug or any excipient, leptomeningeal carcinomatosis, tuberculosis.

NOTE: Patients with vitiligo, Grave's disease, or psoriasis not requiring systemic treatment (within the past 2 years) are not excluded.

- 6. Female patients who are pregnant, breast-feeding or male or female patients of reproductive potential who are not employing an effective method of birth control
- 7. Any condition that, in the opinion of the investigator, would interfere with evaluation of the study drug or interpretation of patient safety or study results.

Study Drug, dosage and mode of administration

The recommended dose of Durvalumab is 10 mg/kg administered as an intravenous infusion over 60 minutes every 2 weeks, until disease progression or unacceptable toxicity. Dose escalation or reduction is not recommended. Dose withholding, or discontinuation may be required based on individual safety and tolerability.

Durvalumab will be supplied as either 500 mg (500mg/10mL) or 120 mg (120 mg/2.4mL) single-dose vial and does not contain any preservatives, aseptic technique must be observed. Administer infusion solution intravenously over 60 minutes through an intravenous line containing a sterile, low-protein binding 0.2 or 0.22 micron in-line filter.

Duration of treatment

The Treatment Phase will extend from start of Week 0 to end of week 20, Day 141; or until study drug discontinuation due to either disease progression or unacceptable toxicity; or other reasons whichever occurs earlier, as listed in Section 7.1. Patients may continue to receive durvalumab as long they are continuing to show clinical benefit, as judged by the investigator, and in the absence of discontinuation criteria.

Post-trial access

Patients who are observed to receive clinical benefit from durvalumab at the end of week 20 may continue get the drug free of cost (provided by AstraZeneca) to all the responding patients until unacceptable toxicity/disease progression or as per the decision of the treating physician

Safety Evaluations

Safety evaluations will include adverse event monitoring, physical examinations, ECG monitoring, clinical laboratory parameters (hematology and biochemistry), vital sign measurements, and WHO performance status and death as observed by the investigator. Based on the previous human experience with durvalumab, in vitro studies, and animal toxicological

Study Code - D133HC00003 Version 4.1, Date: 12 October 2022 findings immune mediated pneumonitis hepatitis colitis a

findings, immune mediated pneumonitis, hepatitis, colitis and endocrinopathies will be closely monitored. Any of the safety monitoring assessments may be performed more frequently, and adverse events should be evaluated by the investigator according to the standard practice if clinically indicated.

Statistical methods

Sample Size Justification

The primary endpoint of the trial is to demonstrate the safety profile of durvalumab in routine clinical practice as assessed by the incidence of adverse events (AEs) (Serious and Non-serious AEs) observed during trial. Based on the Durvalumab historic data, estimated proportion of 31% for adverse events prevalence rate. With a sample size of 83, would be able to achieve the 10% precision of the estimates with the 95% level of confidence. Approximately 120 participants will be screened to achieve around 100 participants enrolled in the study.

Scenario#	estimated proportion	Precision	Confidence level	Required sample size
1	31%	.15	95%	37
2	31%	.14	95%	42
3	31%	.13	95%	49
4	31%	.12	95%	58
5	31%	.11	95%	68
6	31%	.10	95%	83

Hypothesis

No formal hypothesis testing will be conducted.

Statistical Analysis

Data will be summarized using descriptive statistics. Continuous variables will be summarized using the number of observations, mean, SD, median, and range as appropriate. Categorical values will be summarized using the number of observations and percentages as appropriate.

The safety analysis population will include all patients who sign the ICF and receive at least one dose of durvalumab.

Adverse Events (both in terms of MedDRA preferred terms and CTCAE grade) will be listed individually by patient. Any AE occurring before treatment with durvalumab will be included in the data listings but will not be included in the summary tables of AEs.

[figure not shown]
Any AE occurring within 90 days of discontinuation of investigational product (ie, the last dose of durvalumab) will be included in the AE summaries. Any events in this period that occur after a patient has received further therapy for cancer (following discontinuation of durvalumab) will be flagged in the data listings.

The study is designed in accordance with the Health Authority requirements in India. It is intended to provide information regarding the safety profile for patients in India and will contribute additional information to the overall safety profile of durvalumab. Due to the small sample size, this study should not be directly compared to the data from any other country.

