6.7 Post-trial Access

Patients who are observed to receive clinical benefit from durvalumab at the end of week 20 may continue get the drug free of cost (provided by AstraZeneca) to all the responding patients until unacceptable toxicity/disease progression or as per the decision of the treating physician

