
Table 14.1.4.2 Summary of History of Tobacco (Enrolled Analysis Set)

	Durvalumab
	N = xxx
	n (%)
Smoking History	
Current	xx (xx.xx)
Past	xx (xx.xx)
Never	xx (xx.xx)

- The Capital "N" in the column header represents the total number of patients in Enrolled Analysis Set.
- The small "n" in summary statistic represents the total number of patients in the row category.
- Percentages are based on total number of patients in Enrolled Analysis Set.
- Source: Listing 16.1.6.2
- Table Name: xxxxx

Document Title:	Document ID:	BP04-01
Statistical Analysis Plan	Version Number:	3.1
Statistical Analysis Plan	Effective Date:	25-Nov-2021

Table 14.1.5.1 Summary of IP Administration (Enrolled Analysis Set)

	Durvalumab
	N = xx
Visit 2	
Total Dose Administered(mg/mL)	
n	Xx
Missing	Xx
Mean (SD)	xx.x (xx.xx)
Median	xx.x
(min, max)	(xx.xx, xx.xx)
Dose interrupted during infusion, n (%)	
No	xx (xx.xx)
Yes	xx (xx.xx)
Dose Restarted, n (%)	
Yes	xx (xx.xx)
No	xx (xx.xx)

- The Capital "N" in the column header represents the total number of patients in Enrolled Analysis Set.
- The small "n" in summary statistic represents the total number of patients in the row category.
- Percentages are based on number of patients in Enrolled Analysis Set.
- SD = Standard Deviation, min=minimum, max=maximum
- Source: Listing 16.1.4.1 and Listing 16.1.4.2
- Table Name: xxxxx
- Programmer Note: Continue the above table from Visit 2 to Visit 11.

Document Title:	Document ID:	BP04-01
Statistical Analysis Plan	Version Number:	3.1
	Effective Date:	25-Nov-2021

Table 14.1.5.2 Summary of Study drug Administration accountability (Enrolled Analysis Set)

	N = xx
At Visit 11,	
Dose Reduced in any of the Visit , n (%)	
Yes	xx (xx.xx)
No	xx (xx.xx)
Dosing Completed, n (%)	
Yes	xx (xx.xx)
No	xx (xx.xx)
Number of IV Dose administered in the treatment period	
n	Xx
Missing	Xx
Mean (SD)	xx.x (xx.xx)
Median	xx.x
(min, max)	(xx.xx, xx.xx)
Unused IP returned, n (%)	
Yes	xx (xx.xx)
No	xx (xx.xx)
Compliance (%)	
n	Xx
Missing	Xx
Mean (SD)	xx.x (xx.xx)
Median	xx.x
(min, max)	(xx.xx, xx.xx)

- The Capital "N" in the column header represents the total number of patients in Enrolled Analysis Set.
- The small "n" represents the total number of patients in the row category.
- All Percentages rows are based on number of patients in Enrolled Analysis Set.
- SD = Standard Deviation, min=minimum, max=maximum
- Source: Listing 16.1.4.3
- Table Name: xxxxx

Document Title:	Document ID:	BP04-01

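### After the End-of-Evaluation visit, events on and off durvalumab are pooled, and no planned visit, listing or table captures later dosing or new cancer therapy

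*Protocol*

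**What the plan says.** **Treatment.** Protocol 1.2 (Overall design) states: "The treatment period for this study is 20 weeks, which corresponds to 10 doses of study drug administration". Patients still benefiting at the end of Week 20 "will continue treatment in post-trial phase (defined in section 6.7"). Under section 6.7 that supply runs "until unacceptable toxicity/disease progression or as per the decision of the treating physician", so it has no fixed end.

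**Follow-up.** Protocol 1.2 (Follow Up Phase) states: "A telephonic follow-up will be conducted 90 days after the EOE Visit". Total observation is "up to a maximum duration of approximately 230days for each patient". In the Schedule of Activities (protocol Table 1, repeated in SAP 2.2.5), the Visit 13 column, Day 230, sits under the follow-up period and has one mark, AE/SAE assessment. Study drug is marked at Visits 2 to 11 and concomitant medication up to Visit 12.

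**AE window.** Three texts differ:
- The synopsis (Statistical Analysis) states: "Any AE occurring within 90 days of discontinuation of investigational product (ie, the last dose of durvalumab) will be included in the AE summaries". It also wants events after further cancer therapy flagged in the listings.
- Protocol 8.2.2 attaches the 90-day follow-up collection to patients who stop before 20 weeks.
- The footnote to SAP Table 14.2.1.1 defines a treatment-emergent event as one after the first dose, with no end point. The SAP Introduction says that its differences override the protocol's analysis text.

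**Exposure output.** SAP Table 14.1.5.1 runs from Visit 2 to Visit 11. SAP Table 14.1.5.2 reports "Number of IV Dose administered in the treatment period".

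**The concern.** Safety is the trial's only objective. From the EoE visit on, the follow-up period holds two kinds of patient: those still receiving durvalumab through post-trial access and those who have stopped. The planned data do not separate them. No scheduled visit collects durvalumab dosing after Visit 11 or new anticancer therapy after Visit 12. The SAP's infusion listings are keyed to visits, and its AE listings have no column for continued durvalumab or for the further-therapy flag.

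A reader of the final AE tables would therefore see events from up to about Day 230 beside a dose count that stops at 10. The reader could not tell how many patients were still on drug when those events were being collected. Such events are plausible: protocol 4.2 cites pneumonitis onset on durvalumab ranging from 1 to 406 days.

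**Working it through.** **1. The plan's own dates.** Doses fall on Days 1 + 14k for k = 0 to 9, so the tenth is on Day 127, as in the Schedule of Activities. EoE is Day 141. The call is due at 141 + 90 = Day 231, against the stated Day 230. The difference is within the ±3-day window and the protocol's own approximation.

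**2. Span affected, for patients who reach Week 20.** Days 142 to 230 are 230 − 141 = 89 days, and 89/230 = 39% of observation.

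**3. Doses outside the planned count.** Assume two-weekly dosing continues from Day 141 with none missed. The documents give no post-trial schedule, so this is an upper bound.
- Doses on Days 141, 155, 169, 183, 197, 211 and 225: (225 − 141)/14 + 1 = 7.
- Total 10 + 7 = 17, of which 7/17 = 41% have no planned record.
- The share continuing is not given. If 30% to 90% of 100 patients continued (assumed), at most 30 × 7 = 210 to 90 × 7 = 630 doses would be uncounted.

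**4. Where the 90-day rule can be applied.**
- *Stopped before Week 20:* the last dose is at a scheduled dosing visit, so the cut-off can be computed.
- *Completed 10 doses, none after:* the cut-off is 127 + 90 = Day 217 (214 to 220 with the visit window). Of the 89 days, 217 − 141 = 76 are inside and 230 − 217 = 13 are outside.
- *Dosed on or after Day 141:* the cut-off is 141 + 90 = Day 231 or later. All 89 days are inside, whichever later dose was the last.

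The rule is therefore undetermined only for completers whose post-trial status is unknown, and only for Days 218 to 230, which is 13/89 = 15% of the span. On the same assumed shares, and treating every non-continuer as a completer who stopped at dose 10, that window holds (100 − 90) × 13 = 130 to (100 − 30) × 13 = 910 patient-days.

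**5. What the SAP would count.** Its definition has no end date and takes precedence, so its totals do not depend on the 90-day rule. Every event after the first dose enters the same table, on drug or off.

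**6. Who is followed.** The Schedule of Activities and the Follow Up Phase text schedule the call without restriction. Overall design (1.2) and section 8.2.2 describe post-treatment follow-up only for patients who stop before Week 20. On the first reading the pooling occurs. On the second, events in completers after Day 141 are not systematically collected, yet any that are reported still enter the SAP tables.

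**The case against.** Several points on the other side stand.

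- A reader might infer that the 90-day rule cannot be applied at all. It can, for early discontinuers and for anyone dosed on or after Day 141. The gap is 13 days in one subgroup, and the SAP does not use the rule.
- A reader might infer that later dosing is simply not recorded. Section 6.4 requires changes to dosing and discontinuations in the eCRF, section 6.5 requires medication received during the study to be recorded with dates, and sections 8.2.3 and 8.2.4 attach action taken and causality to each AE. What the documents support is narrower: no visit, listing or table provides for it. The per-AE fields exist only where there is an AE, so they give neither the number of patients still on drug nor the time since last dose.
- A reader might infer that section 4.2 undertakes to separate late-onset events from events under continued dosing. It does not. It says that a 141-day treatment phase allows incidence to be detected, and all its listed median onsets (36 to 91 days) fall inside that phase.
- The SAP dose count is labelled as belonging to the treatment period, so 10 is not a misreported total.
- The study is single-arm and descriptive. Continuers are selected for benefit, so comparing them with patients who stopped cannot establish cause.

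These points narrow the concern but do not remove it: the planned AE output after EoE still cannot be read against exposure.

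**Conclusion.** The point holds in this form. After EoE the follow-up mixes patients on and off durvalumab, neither the visit schedule nor the SAP output provides for dosing after Visit 11 or new cancer therapy after Visit 12, and the open-ended SAP definition pools the events. For patients who reach Week 20 the span is 89 of about 230 days. The 7 uncounted doses per patient are a maximum that rests on uninterrupted two-weekly dosing from Day 141, and the total effect depends on a continuing share that the documents do not give.

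The synopsis's flag for events after further cancer therapy has no scheduled data source at Visit 13. The size of the pooling also depends on how the protocol's conflict over follow-up of completers is settled. This is a low-cost improvement to how the sole endpoint can be interpreted. It does not make the AE totals invalid.

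**What to change.** 1. Add to the Visit 13 call: durvalumab continued after EoE (yes/no), number of further doses, date of last dose, and any other anticancer therapy with its start date. Carry these into a listing, and add the further-therapy flag to the AE listings.
2. In SAP 6.3.1, show AEs, SAEs, AEs of special interest and deaths separately for first dose to EoE and for after EoE to the End-of-Study call. Split the second period by continuing versus stopped durvalumab, with the number of patients in each group, and label the split descriptive. Anchor it on each patient's own EoE visit rather than Day 141, because for early discontinuers the last visit counts as EoE.
3. Reconcile the AE window across the synopsis (Statistical Analysis), protocol 8.2.2 and the footnote to SAP Table 14.2.1.1. State whether patients who complete 20 weeks are followed for AEs to the End-of-Study call, since the Schedule of Activities and Follow Up Phase text conflict with Overall design and section 8.2.2.

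The cost is a few eCRF fields on a contact already scheduled and one further split of planned tables. No visit or procedure is added. The split will not support a causal comparison.
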